5.2 Secondary Outcomes

- 5.2.1 Overall survival (OS), defined as the duration of time from the start of treatment to date of death or date of last contact; those lost to follow-up will be censored.
- 5.2.2 Investigational Agent Safety To determine incidence of adverse events (AEs), serious adverse events (SAEs), and any laboratory abnormalities of each investigational agent tested.
- 5.2.3 To measure response rate of treatment based on a simplified selection methodology using the NGS results.

5.3 Planned EHR Data Collection

The following data points will be collected. The NGS data will consist of the clinical NGS data report, sequence variant reports (example: VCF or variant call files), binary DNA sequence alignment data (BAM files or SAM files), and any quality control reports supporting the validity of the clinical NGS data. The accompanying clinical data will be extracted from the clinical records (through manual and automated processes) and will include demographic information, diagnoses, and medical treatments in addition to information regarding the relationship of NGS to treatment decisions.

- Age, gender, ethnicity, race, insurance type and coverage
- Marital status
- Occupation
- Educational level
- Military service
- Family medical history
- Patient's medical history
 - Previous cancer diagnoses and treatments
 - Previous or current conditions
 - Current prescription medications
- Treating physician and physician ordering tumor DNA sequencing
- Extent of financial assistance provided if applicable
- Vendor used for tumor DNA sequencing

ClinicalTrials.gov: NCT04111107

- Previous and current tobacco and alcohol use information if available
- The date of DNA sequencing results and date of results discussion
- If NGS data revealed somatic mutations warranting further investigation by Genetic Counseling, the type of mutation present and the referral date to Genetic Counseling
- Type of treatment plan toward mutation of interest if applicable/known
- Response and progression-free survival for last known treatment
- Progression-free and overall survival times for new targeted therapy
- Response to new targeted therapy

6.0 Treatment Plan

Patients with actionable tumor mutations who have failed at least two lines of standard of care therapy or are unable or unwilling to receive standard therapy and consent to participate will be included. Patients will be treated according to the following algorithm:

- 1) Next Gen Sequencing report obtained as Standard of Care, preferably within the t 3 months but necessarily within 12 months prior to of enrollment date will be used . If more than one report exists in this time period, the most recent report will be used.
- 2) Patients will be stratified according to whether their NGS assay reports mutation frequency or not.
- 3) If the assay reports mutation frequency and more than one molecular abnormality is identified as actionable the first mutation selected for treatment will be the mutation with the reported highest frequency, with subsequentl selections being in order of frequency from highest to lowest.
 - a. If two or more actionable mutations are reported to have the same frequency then, of these, the mutation selected for protocol treatment shall be chosen via randomization, as described in 4b-4d below..
 - b. If both mutations and amplifications are reported, mutations shall be selected before amplifications.
 - c. If two or more amplifications are reported, they shall be selected in the order of greatest to least amplification.
 - d. If two or more amplifications are reported to have the same degree of amplification, of these theamplification selected for protocol treatment shall be chosen via randomization table as in 4b-4d below.
- 4) If the assay does not report mutation frequency the initial actionable mutation selected will be randomly assigned (in a manner to balance the likelihood of a mutation being selected) as follows:
 - a. If there is a single actionable mutation that mutation will be selected
 - b. If there are 2-5 actionable mutations patient will be randomly assigned a number from 1-5 and the first mutation selected will be the mutation corresponding to the randomly assigned number. If the randomly assigned number is greater than the

Precision medicine for patients with identified actionable mutations at Wake Forest Baptist
Comprehensive Cancer Center (WFCCC): A pragmatic trial
WFCCC # 04519

ClinicalTrials.gov: NCT04111107

- number of actionable mutations, the last listed actionable mutation will be selected.
- c. If there are 6-10 actionable mutations patient will be randomly assigned a number from 1-10 and the first mutation selected will be the mutation corresponding to the randomly assigned number. If the randomly assigned number is greater than the number of actionable mutations, the last listed actionable mutation will be selected.
 - d. If there are 11-15 actionable mutations patient will be randomly assigned a number from 1-15 and the first mutation selected will be the mutation corresponding to the randomly assigned number. If the randomly assigned number is greater than the number of actionable mutations, the last listed actionable mutation will be selected.
 - e. If there are greater than 15 actionable mutations patient will be randomly assigned a number from 1-20 and the first mutation selected will be the mutation corresponding to the randomly assigned number. If the randomly assigned number is greater than the number of actionable mutations, the last listed actionable mutation will be selected.
 - f. If mutations and amplifications of different genes are reported, each shall be counted as an actionable mutation.
- 5) Noting that 87.9% of our patients have 20 or fewer mutations identified, of which many are not actionable, it is anticipated that in almost all patients, the probably of an actionable mutation being selected will be balanced
- 6) Patients will be randomly assigned a second "Treatment Number" from 1-6. 1-6 because it is rare for there to be more than 6 drug options for the treatment of an actionable mutation. This will be used to select the first chosen drug for treatment of a actionable mutation.
- 7) Once an actionable mutation is selected, if more than one drug is listed as a possible treatment, the drug(s) corresponding to the patient's Treatment Number listed in the tumor analysis report for the selected mutation will be selected as treatment. Patients must have adequate organ and marrow function to permit administration of the study drug as specified in the drug packaging label. If the subject has a medical contraindication to the selected drug (according to the drug label) or the selected drug(s) cannot be obtained for the patient, the study team will select the next drug(s) presented by the tumor sequencing report. If necessary, this process will be repeated until a suitable drug is selected, returning to the top of the list of the drugs listed for the selected mutation if necessary. If the list of drugs proposed for the selected actionable mutation is exhausted, then the next listed actionable mutation will be selected and the process repeated, if necessary returning to the top of the list of actionable mutations if the first selected mutation is not at the top of the list on the report. Documentation for why particular drugs were not selected, if applicable, will be obtained for alternative

[figure not shown]
Patient has NGS performed as prescribed by their doctor and/or is entered in the Precision Medicine RegistryCCCWFU 04218 IPR00054757

and has failed at least **Is the Mutational Frequency listed on the NGS Report?** receive standard therapy

Precision medicine for patients with identified actionable mutations at Wake Forest Baptist
Comprehensive Cancer Center (WFBCCC): A pragmatic trial
WFBCCC # 04519

ClinicalTrials.gov: NCT04111107

therapies in order to evaluate some of the potential barriers to treatment using the NGS method.

If NGS report lists the mutational frequency, targeted mutation will be the highest frequency mutation

Precision medicine for patients with identified actionable mutations at Wake Forest Baptist Comprehensive Cancer Center (WFBCCC): A pragmatic trial
WFBCCC # 04519

If no mutational frequency listed on NGS report, the actionable mutations will be assigned, in the manner below (based on their presentation in the NGS report):

If single actionable mutation is identified	2-5 actionable mutations	6-10 actionable mutations	11-15 actionable mutations	>-15 actionable mutations
Single Actionable Mutation will be targeted	
Patient randomly assigned number from (1-5). Mutations assigned a number chronologically, starting with first presented mutation, #1. The mutation number that is the same as the randomly assigned patient number will be targeted. For example, for patient randomized to the number 5, the 5th mutation will be targeted.
 
If randomly assigned number is greater than number of actionable mutations, the last listed actionable mutation will be selected.
	
Patient randomly assigned number from (1-10). Mutations assigned a number chronologically , starting with first presented mutation,#1. The mutation number that is the same as the randomized patient number will be targeted. For example, for patient randomized to number 7, the 7th mutation will be targeted.
	
Patient randomly assigned number from (1-15). Mutations assigned a number chronologically starting with the first mutation,#1. The mutation number that is the same as the randomized patient number will be targeted. For example, for patient randomized to number 15, the 15th mutation will be targeted.
 
If randomly assigned number is greater than number of actionable mutations, the last listed actionable mutation will be selected.
	
Patient randomly assigned number from (1-20). Mutations listed on the report will be assigned a number starting with the first mutation,#1. The mutation number that is the same as the randomized patient number will be targeted. For example, for patient randomized to number 19, the 19th mutation will be targeted.
 
If randomly assigned number is greater than number of actionable mutations, the last listed actionable mutation will be selected.

All Patients will be randomly assigned a second “Treatment Medication Number” from 1-6. (it is rare for more than 6 drug options for the treatment of an actionable mutation.)

If more than one drug is listed as possible treatment, the drug corresponding to the patient's Treatment Number (listed in the tumor analysis report for the selected mutation) will be selected as treatment. If drug is contraindicated or unattainable for the patient,-the next drug on the list will be selected.

Precision medicine for patients with identified actionable mutations at Wake Forest Baptist Comprehensive Cancer Center (WFBCCC): A pragmatic trial
WFBCCC # 04519

Study-Related Activities

	Pre-Study ^a	Cycle 2, Day 1	Day 1; every even cycle (after cycle 2)	End of Treatment ±7 days	Follow up for Safety (30+ days after last treatment) required only if pt has treatment related AEs at end of treatment visit
Informed Consent	X				
Demographics	X				
Medical History	X				
Concurrent Meds	X				
Physical Exam	X	X	X	X	X
Vital Signs	X	X	X	X	X
Performance Status	X	X	X	X	X
Bone Marrow Biopsy ^h	X	X	X	X	
Imaging ^d	X	X	X ^f	X	
CBC w/diff, platelets ^e	X	X	X	X	X
Serum Chemistry ^b	X	X	X	X	X
B-HCG ^c	X				
Dose Adjustment Form		X	X		
Adverse Event Evaluation		X	X	X	X
Survival Status/Telephone Follow up ^g					X
PROMIS 29	X	X		X	
Satisfaction with Medical Decision Scale	X	X		X	
Patient Reported Outcome- Demographics/Health Literacy	X				

^a Pre-study requirements listed in table must be completed **within** 30 days prior to registration. Imaging demonstrating disease progression should be completed within 60 days of registration. Imaging should be repeated if the scan occurred more than 30 days prior to treatment initiation..

^b Albumin, alkaline phosphatase, total bilirubin, bicarbonate, BUN, calcium, chloride, creatinine, glucose, potassium, total protein, SGOT[AST], SGPT[ALT], sodium.

^c Serum pregnancy test within 10 days of Pre-study visit (women of childbearing potential only).

^d Imaging will be performed as part of SOC for solid tumors every other cycle, however due to patients on different drug treatment regimen, this may occur at 6 weeks ±2 weeks, 8 weeks ± 2 weeks or 12 weeks ± 2 weeks. Not required for leukemias. As clinically indicated in Multiple myeloma.

^e Labs will be performed in accordance with the recommendations of the prescribing instructions for the drug that is utilized

^f If treatment is discontinued for reasons other than progression, imaging will be performed on the same schedule as was utilized while patient was receiving treatment until progression.

^g Survival and information related to cancer treatment received after the study and disease status is monitored bimonthly via telephone contact or EMR review after treatment termination. Medical record review will be performed to coincide with the bimonthly telephone call to obtain information regarding evidence and of relapse (as documented on CT, PET, biopsy, etc).

^h If clinically indicated bone marrow biopsy will be repeated to evaluate response to therapy.

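### The random draw in steps 4b–4e favours the last mutation on the list at 15 of the 19 list lengths from 2 to 20, contrary to the balance the plan states

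*Combined protocol and SAP*

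**What the plan says.** Section 6.0 sets out how the mutation to be treated first is chosen. When the assay does not report mutation frequency, step 4 says the mutation is "randomly assigned (in a manner to balance the likelihood of a mutation being selected". A single actionable mutation is simply taken (4a). Longer lists use a draw from a range set by band. Step 4b reads "If there are 2-5 actionable mutations patient will be randomly assigned a number from 1-5"; 4c uses 1–10 for 6–10 mutations, 4d uses 1–15 for 11–15, and 4e uses 1–20 for more than 15. Each of these steps carries the same overflow rule: "If the randomly assigned number is greater than the number of actionable mutations, the last listed actionable mutation will be selected". The selection chart in Section 6.0 repeats it ("If randomly assigned number is greater than number of actionable mutations, the last listed actionable mutation will be selected") for the 2–5, 11–15 and over-15 bands; its 6–10 cell omits the sentence that step 4c contains.

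Ties use the same mechanism. For equal mutation frequency, step 3a says "the mutation selected for protocol treatment shall be chosen via randomization, as described in 4b-4d below"; for equal amplification, step 3d says "chosen via randomization table as in 4b-4d below".

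Step 5 notes that 87.9% of the centre's patients have 20 or fewer mutations, many of them not actionable, and concludes that "it is anticipated that in almost all patients, the probably of an actionable mutation being selected will be balanced".

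**The concern.** The ranges are fixed by band, but the list length varies within a band. Every number above the patient's own count goes to one mutation, the one printed last. That is a weighted draw, and the weight depends on how far the list falls short of the top of its band.

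This matters because of what the trial is testing. Section 14.1 says the object of evaluation is the approach to assigning treatment and not any particular drug, and Section 1.0 describes that approach as balanced. If the rule does not balance selection, a report that repeats the protocol's description will misdescribe the intervention.

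**Working it through.** **Inputs** (all from Section 6.0). Let k be the number of actionable mutations on the report and m the top of the draw range: m = 5 for k = 2–5, m = 10 for k = 6–10, m = 15 for k = 11–15, and m = 20 for k above 15.

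**Assumption.** Each number from 1 to m is equally likely. The protocol says the number is randomly assigned and gives no weights.

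**The plan's own figure.** No probability is printed. The stated property is balance, which for k mutations means 1/k each.

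**Formula.** The selected position is the smaller of the draw and k. For k up to m:

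- P(each entry except the last) = 1/m
- P(last entry) = (m − k + 1)/m
- ratio of last to any other = m − k + 1

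The ratio is 1 only when k = m. Example, k = 2: P(first) = 1/5 = 20%, P(last) = (5 − 2 + 1)/5 = 4/5 = 80%.

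| k | m | Last entry | Each other entry | Equal share (1/k) | Ratio |
|---|---|---|---|---|---|
| 2 | 5 | 80% | 20% | 50% | 4 |
| 3 | 5 | 60% | 20% | 33.3% | 3 |
| 4 | 5 | 40% | 20% | 25% | 2 |
| 5 | 5 | 20% | 20% | 20% | 1 |
| 6 | 10 | 50% | 10% | 16.7% | 5 |
| 7 | 10 | 40% | 10% | 14.3% | 4 |
| 8 | 10 | 30% | 10% | 12.5% | 3 |
| 9 | 10 | 20% | 10% | 11.1% | 2 |
| 10 | 10 | 10% | 10% | 10% | 1 |
| 11 | 15 | 33.3% | 6.7% | 9.1% | 5 |
| 12 | 15 | 26.7% | 6.7% | 8.3% | 4 |
| 13 | 15 | 20% | 6.7% | 7.7% | 3 |
| 14 | 15 | 13.3% | 6.7% | 7.1% | 2 |
| 15 | 15 | 6.7% | 6.7% | 6.7% | 1 |
| 16 | 20 | 25% | 5% | 6.25% | 5 |
| 17 | 20 | 20% | 5% | 5.9% | 4 |
| 18 | 20 | 15% | 5% | 5.6% | 3 |
| 19 | 20 | 10% | 5% | 5.3% | 2 |
| 20 | 20 | 5% | 5% | 5% | 1 |

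The stated balance is reproduced at 4 lengths (5, 10, 15, 20) and fails at the other 15. The last entry has an outright majority only at k = 2 and 3. Of every 100 patients drawn with k = 2, 80 are expected to start at the last entry, where balance would give 50.

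**Above 20.** The draw stops at 20, so positions 1–20 have 1/20 = 5% each and later positions have 0. At k = 22, two mutations cannot be selected first.

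**Ties.** Counting the tied alterations as k, which is the natural reading of 3a and 3d, a two-way tie splits 80/20.

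**Step 5's reason.** A count of 20 or fewer ensures only that every listed mutation can be drawn. It does not make the chances equal, as the table shows. The remark that many mutations are not actionable does not help either: shorter lists include k = 2 and 3, where the last entry's share is largest. (Section 1.0 attaches the same 87.9% to 20 or more mutations; step 5's version is used here.)

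**Later steps.** Step 7 moves a patient on only when the drugs for the selected mutation are contraindicated or cannot be obtained: "then the next listed actionable mutation will be selected and the process repeated". It follows list order and does not restore equal chances. No redraw is described.

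**The case against.** The strongest reply is that little depends on this. Section 14.2 describes a non-randomized, single-arm trial whose primary analysis is a within-patient ratio tested against 1.0. No planned analysis compares mutations or drugs for efficacy or uses selection probabilities. An unequal rule that is fully written down can still be reproduced, so correcting the word balanced might be enough. This stands as a limit on the consequence: no bias in the progression-free ratio has been shown. It does not remove the conflict between step 4's stated aim and its mechanism.

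Second, step 5 speaks of almost all patients, not of list lengths. Patients with one actionable mutation, and those ranked by frequency without ties, are untouched. The documents give no distribution of actionable counts, so the share affected is unknown, and 15 of 19 must not be read as a share of patients. That is right. What the check shows is that step 5's reason does not deliver the balance it asserts.

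Third, 3a and 3d do not say expressly whether the band is set by the number tied or by the patient's total. The 80/20 figure rests on the first reading. On the other, with overflow still going to the last of a tied pair, a total of 6–10 would give (10 − 2 + 1)/10 = 90%, which is no closer to balance.

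**Conclusion.** The concern holds. As written, steps 4b–4e do not balance first selection except at k = 5, 10, 15 and 20. At the other 15 lengths from 2 to 20 the last entry is 2 to 5 times as likely as any other, with the extreme share of 80% at k = 2, and above 20 the later entries are excluded from first selection. This contradicts step 4's aim and the description in Section 1.0, and step 5's argument does not repair it.

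The result assumes equally likely draws. It covers first selection in patients with two or more actionable mutations whose assay reports no frequency, and ties under 3a and 3d. The correction should be made, but nothing here shows that the primary result would change.

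**What to change.** Replace the banded draws in 4b–4e, and the tie rules 3a and 3d that refer to them, with one uniform draw from 1 to k, where k is the number of actionable (or tied) alterations on that patient's report. Each then has probability 1/k at every length, including above 20. Delete the overflow rule from the text and the selection chart, and correct step 5.

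The cost is a change to the registrar's randomisation tool and an amendment to the text and chart. The registrar already needs k to choose the band, and no patients or procedures are added. If enrolment has begun, the trial will contain two assignment rules: record which rule assigned each patient in one extra field, and describe the earlier rule accurately in the report. If the sponsor prefers to keep a single rule throughout, the minimum is to remove the claims of balance and state the actual probabilities; that cures the misdescription but not the imbalance.

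Two separate points belong in the same amendment. The Schema (one 1–20 draw, drug level 1–4) and Section 6.0 (banded draws, Treatment Number 1–6) must be reconciled. The plan should also state what happens when the Treatment Number exceeds the number of drugs listed; step 7's return to the top of the drug list is worded only for drugs that are contraindicated or unobtainable.

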1.0 Introduction and Background

Precision medicine is a rapidly growing field with the potential to bypass ineffective treatments and target specific genetic mutations present in cancer cells. Although clinicians have access to increasing amounts of data regarding tumor genomics, it can be problematic to identify a primary driver mutation and the optimal treatment.(Paolillo, Londin, & Fortina, 2016). Due to this complexity many clinicians are uncomfortable interpreting genomic sequencing results from next generation sequencing assays (“NGS”) [J. Clin Oncol 2014, 32, 1317-1323]. A recent survey of providers at a major academic center revealed that more than half the providers were uncomfortable interpreting the information from a genomic test [Oncotarget 2017; 8; 27145-27154]. Various strategies have been used to facilitate the proper interpretation of genomic data including in-person and virtual molecular tumor boards but the limited experience and large numbers of permutations with multiple genetic mutations in a single tumor make the identification of one or more driver mutations in a particular patient largely a matter of an educated guess at best. This has the effect of discouraging the use of targeted therapies, that may provide benefit, in patients who have exhausted standard of care treatments. Frequently, physicians prescribe medications off-label in an effort to delay progression of disease. Off label prescribing involves prescribing a medication for an indication other than the condition for which there is FDA approval.Those physicians prescribing targeted therapies off label, based on NGS results face other challenges. These include lack of access to available drugs, costs of available drugs, and differing reimbursement policies among insurance companies, among others (Messner et al., 2016)

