2.0 Objectives

2.1 Primary Objective

- 2.1.1 To estimate the progression-free ratio, as defined by the progression-free survival time on study treatment divided by the progression-free survival time on the last treatment received by patient, for an identified actionable mutation, who will be treated with an off-label treatment off label therapy based on a simplified selection methodology using the NGS results.

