2.2 Secondary Objectives

- 2.2.1 To estimate patient response rate on off-label treatments for actionable mutations based on NGS results.
- 2.2.2 To estimate overall survival (OS) for patients treated with off-label treatments for actionable mutations based on NGS results.
- 2.2.3 To describe the safety of using off-label or other experimental treatments for patients with actionable mutations based on NGS results.

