3.0 Patient Selection

3.1 Inclusion Criteria

- 3.1.1 Cancer patients at Wake Forest Baptist Comprehensive Cancer Center and its satellites who have next generation DNA sequencing results on their tumor biopsy or surgically resected tissue and/or blood samples and/or consent to the WFCCC Precision Oncology Registry to use their information for research.
- 3.1.2 Actionable mutation (defined as a mutation or gene amplification for which an off-label therapy is identified on the patient's NGS report for which NCCN guidelines do not recommend a specific treatment in the particular disease or for which there is no documentation in the patient's medical record of clinical data demonstrating lack of activity with the targeting of the specific mutation or amplification in the patient's specific disease) uncovered by the genomic sequencing of a tumor or those that have undergone liquid biopsy assay of their tumor genomic, performed by Wake Forest or another and who are medically able to receive targeted therapy based on those results.
- 3.1.3 Sequencing on a sample collected within 3 months prior to registration is strongly encouraged but must have been performed within the 12 months prior to registration.
- 3.1.4 Patients must have progressed through at least two lines of treatment, or are not candidates for or unwilling to receive any standard therapies. Patients who have received treatment on the present protocol who have progression of disease may be recruited to the trial for treatment using another targeted therapy provided that they fullfil the other criteria for participation in the trial. If a patient discontinues treatment on this protocol they can be considered for further participation in this trial provided they meet all of the eligibility criteria and are eligible for re-registration and re-consent.
- 3.1.5 ECOG of ≤ 3
- 3.1.6 Life expectancy of greater than 6 weeks

ClinicalTrials.gov: NCT04111107

3.1.7 The effects of the drugs used for cancer treatment on the developing human fetus are unknown. For this reason and because of the possibility that the agents are teratogenic, women of child-bearing potential and men must agree to use adequate contraception (hormonal or barrier method of birth control; abstinence) prior to study entry and for the duration of study participation. Should a woman become pregnant or suspect she is pregnant while participating in this study, she should inform her treating physician immediately.

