6.1.4 Investigational agent

The investigational agent in this protocol will be an FDA approved targeted therapy that target specific mutations in specific disease.

Supportive care regimens will vary depending on the type of drug that will be administered at the treating physician's discretion.

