10.0 Pharmaceutical Information

10.1 Pharmaceutical Accountability

The targeted off-label chemotherapeutic or immunotherapy agents are commercially available. Their description, use, preparation, administration, storage and stability parameters are outlined in the package insert. Disposal of remaining portions of the agents should be done per the Wake Forest Waste Stream.

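### Inclusion criterion 3.1.2 joins its two limits with 'or', so a mutation documented as inactive in the patient's disease can qualify; a smaller point is that step 7 can assign an on-label drug and label status is not recorded

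*Combined protocol and SAP*

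**What the plan says.** **Eligibility.** Section 3.1.2 defines an actionable mutation as a mutation or amplification with a listed off-label therapy and adds two limits, worded as follows: "for which NCCN guidelines do not recommend a specific treatment in the particular disease or for which there is no documentation". The documentation meant is clinical data, held by the patient's own chart, showing that targeting the change does not work in that disease. Appendix A, the checklist used to confirm eligibility, joins the two limits with the same 'or'.

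**Treatment class in the objectives.** Objective 2.1.1 concerns patients "who will be treated with an off-label treatment off label therapy based on a simplified selection methodology using the NGS results". Objective 2.2.1 is "To estimate patient response rate on off-label treatments for actionable mutations based on NGS results", and 2.2.2 words overall survival in the same way. Section 1.0 explains the term: "Off label prescribing involves prescribing a medication for an indication other than the condition for which there is FDA approval". Section 10.1 also describes the agents as off-label: "The targeted off-label chemotherapeutic or immunotherapy agents are commercially available".

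**Drug assignment.** Under step 7 of section 6.0 the Treatment Number picks a drug from those listed on the report for the selected mutation. The next drug is taken if the patient "has a medical contraindication to the selected drug (according to the drug label) or the selected drug(s) cannot be obtained". The flow chart gives the same two reasons: "If drug is contraindicated or unattainable for the patient". Section 6.1.4 asks for approval, not off-label use: "The investigational agent in this protocol will be an FDA approved targeted therapy that target specific mutations in specific disease".

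**The concern.** The two parts are separate, because NCCN status is not label status.

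The first and more important part is an eligibility rule that gives a wrong result when followed literally. A limit meant to keep out mutations known to be inactive does so only when NCCN also recommends a treatment. Where NCCN is silent, a documented failure of the target in the patient's own disease does not bar enrolment. At stake is a patient with advanced cancer being assigned a drug against a target already recorded as inactive.

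The second part is a mismatch between the objectives and the draw. Three objectives are worded as outcomes on off-label treatment, but no operative rule ensures that the assigned drug is off-label, and neither section 5.3 nor section 11.0 lists a field for its label status. A reader of the results could not tell how far they describe off-label treatment.

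**Working it through.** **1. The criterion as a truth table.** Take it as given that an off-label therapy is on the report. The criterion as written is (NCCN recommends no treatment) or (inactivity not documented).

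| NCCN recommends a treatment | Inactivity documented | As written, 'or' | Plain 'and' | Proposed rule (see fix) |
|---|---|---|---|---|
| no | no | in | in | in |
| no | yes | **in** | out | out |
| yes | no | in | out | in only if that treatment was already received, cannot be received or is declined |
| yes | yes | out | out | out |

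'Or' excludes one of four combinations and plain 'and' excludes three. The second row is the wrong result. The sentence can also be grouped as (off-label therapy listed and NCCN silent) or (inactivity not documented). That grouping excludes three of eight combinations overall, but again one of four once an off-label therapy is listed. The finding does not depend on the grouping.

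**2. Can step 7 assign an on-label drug?**
- Source list: section 1.0 says the report gives known drugs with suspected or proven efficacy for the mutation. Off-label options are among them but are not said to be the only ones.
- Eligibility: 3.1.2 requires that an off-label therapy be listed for the mutation, not that it be the one given. An on-label assignment therefore needs at least two listed drugs.
- Draw: step 7 and the flow chart skip a drug for contraindication or lack of access only. An off-label drug that cannot be obtained is replaced by the next listed drug, whatever its label status.
- Dosing: 6.1.2 doses by an indication in the patient's own organ system where one exists. An organ-system match is not always the same condition, but the plan does foresee such labels.

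So the route is open. The documents do not say how often a list contains an on-label drug.

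**3. A conditional figure for the draw.** Assume one on-label drug among m listed drugs, m from 2 to 6, and a Treatment Number uniform on 1-6 (step 6 and flow chart). Number j selects position j whenever j ≤ m, so each position is drawn first with probability at least 1/6 = 17%, however numbers above m are handled. The schema gives 1-4 instead. Positions 1 to 4 then have at least 1/4, but positions 5 and 6 have no number of their own and the floor fails there.

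**4. Sample size.** Inputs from 14.4: difference 0.3, SD 1.71, two-sided 0.05, power 80%, Wilcoxon test under normality (efficiency 3/π).
- Normal approximation: (1.71 × (1.960 + 0.842) / 0.3)² = 255.0 with unrounded quantiles; divided by 3/π, 267.0.
- Based on t: n = 257; 257 × π/3 = 269.1. Power at 269 is 0.7999, which agrees with the plan's 269 and 80%.
- Recruitment: 269 / 0.8 = 336.25, rounded up to 337, as stated.

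Both figures reproduce, and nothing proposed here changes them. By the same method, an off-label subset would have the power below. The on-label shares are assumed, since the documents give none.

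| Assumed on-label share | Evaluable in subset | Power |
|---|---|---|
| 5% | 269 × 0.95 ≈ 256 | 0.78 |
| 10% | 269 × 0.90 ≈ 242 | 0.76 |
| 20% | 269 × 0.80 ≈ 215 | 0.71 |

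This supports reporting the subset as a sensitivity analysis and not making it primary.

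**The case against.** **On eligibility.** Staff may read 'and' where the text says 'or'. The treating physician signs the checklist, and 3.1.2 also requires that the patient be medically able to have the therapy. Enrolment is therefore not automatic, and that stands. But the checklist repeats the faulty wording, so the document used for the check does not correct it. A stronger objection is aimed at the obvious repair. Plain 'and' would turn away a patient who has already progressed on the NCCN-recommended drug for that mutation and has another off-label agent listed, arguably the patient the trial is for. This also stands, and the fix is shaped by it.

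**On the draw.** Section 14.1 says the trial evaluates a way of assigning treatment, not a particular treatment, so counting everyone assigned is right for the primary analysis. Objective 2.2.3 extends to other experimental treatments, so the objectives do not hold to one strict class. Entry rules narrow the route: patients who enter because they cannot have or do not want any standard therapy are unlikely to take an on-label drug that is itself standard. All of this stands. What remains is a patient with an approved, unused drug after two lines, and three objectives whose wording 14.1 does not reconcile with step 7.

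**Stronger readings that a reader might infer.**
- That on-label drugs must be struck from the draw. The documents do not require this. It would take an approved option away from the patient and largely empty the matching-indication dosing clause in 6.1.2.
- That about one patient in six receives an on-label drug. The 17% applies only if such a drug is listed and Treatment Numbers run 1-6.
- That the PFS ratio is biased in a known direction. Neither the size nor the sign of an effect follows from anything in the documents.

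**Conclusion.** The eligibility wording is wrong as written. Given a listed off-label therapy, 3.1.2 and Appendix A exclude one of four combinations and admit a mutation with documented inactivity in the patient's disease when NCCN is silent. One of four counts logical cases, not patients; how many patients fall in the faulty case is unknown. The conclusion rests on a literal reading of the criterion and holds under either grouping of the sentence.

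The draw is a smaller matter and an inexpensive improvement. Step 7 permits an on-label assignment while 2.1.1, 2.2.1 and 2.2.2 speak of off-label treatment. Its frequency and its effect on the PFS ratio cannot be derived. The primary test as 14.1 frames it is not undermined, and 269 and 337 stand.

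**What to change.** 1. **3.1.2 and Appendix A.** Make it a requirement in its own right, joined by 'and', that the record contains no clinical data showing lack of activity of targeting this mutation or amplification in the patient's disease. Let the NCCN limit be met when NCCN recommends no specific treatment, or when the patient has already received, cannot receive or declines the recommended one.
2. **Label status.** Add one data field: whether the assigned drug was FDA-approved for the patient's condition at the date of assignment, using the section 1.0 meaning. For patients already treated, derive it from the diagnosis (5.3) and the Study Medication Form (11.0).
3. **Objectives and analysis.** Keep the all-assigned analysis in 14.2 and 14.3 as primary, in line with 14.1, and describe it as NGS-selected therapy. Report the PFS ratio, response rate and OS in the off-label subset as a sensitivity analysis. Leave on-label drugs in the draw.

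Cost: a short rewording in two places, one field, a wording change in the objectives and one extra analysis, with no change to the sample size. Slightly fewer mutations will qualify, so the 20-30% share in 14.5, and the 10-15 patients a month that rest on it, should be rechecked.
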